Methods: Approximately 42 patients, between the ages of 18-65 years, will be consecutively recruited to participate in a randomized prospective clinical trial. Enrolled subjects will be randomly allocated into one of 3 groups: Standard Invisalign therapy (G1-control), Accelerated Invisalign therapy + vibration (G2) and Accelerated Invisalign therapy without vibration (G3). Data collection will include intra oral scans of both the maxillary and mandibular dentition at 5 different time points: TO (baseline), T1 (4 days), T2 (14 days), T3 (6 weeks) and T4 (12 weeks). In addition, PerioPaper strips will be used to sample gingival crevicular fluid at each of the time points listed above. Research subjects will also be asked to complete a daily diary regarding their pain level during treatment. Data analysis will be used to specifically evaluate alignment of adjacent teeth and translational, and/or rotational, tooth movement will be evaluated by superimposing digital models recorded at the specific time points. Inflammation biomarkers will be analyzed with ELISA. Finally, the

statistical significance of our data will be evaluated with a 3 way repeated ANOVA as well as a post hoc comparison with Bonferri correction. P values less than .05 will be considered statistically significant.

Specific Aims:

In this study, we propose a randomized prospective clinical design to investigate effects of vibration therapy, using an AcceleDent Aura® device, on the rate of orthodontic tooth movement, activation of gingival crevicular fluid inflammation biomarkers and patient discomfort in conjunction with accelerated Invisalign therapy.

Hypothesis:

We propose vibration therapy will accelerate orthodontic tooth movement, increase inflammation biomarkers and reduce pain for orthodontic patients.

Background:

Align Technology©, Inc. developed Invisalign® in 1997 to meet the esthetic demands of orthodontic patients and providers. Invisalign patients receive a series of computer-assisted designed stereolithic clear retainers to incrementally resolve their malocclusion. Invisalign® and other advances in orthodontic technology such as clear aligners, ceramic brackets and lingual braces offer options to address the esthetic demands of most orthodontic patients but duration of treatment continues to be one of the most challenging aspects of practice.²

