Accelerated orthodontic tooth movement may offer many benefits to both, the patient and the orthodontist. Reduced treatment time reduces the burden of orthodontic treatment by decreasing risk for undesired treatment sequelae (e.g., white spot lesion, caries, gingivitis, etc) and potentially reduces the discomfort commonly associated with orthodontic treatment.¹² Orthodontists benefit from accelerated tooth movement for multiple reasons pertaining to practice management and increased profitability. Orthodontists using accelerated treatment techniques have reported increased profit margins due to reduced chair time and increased organic growth due to differentiation of the practice.²

There are also potential negative outcomes associated with accelerated orthodontic tooth movement. For the patient, there is a potential increased risk for root resorption and increased treatment fees. ² Most orthodontists are charging between \$700-800 for AcceleDent therapy in addition to the normal orthodontic fee. How can Orthodontists expect patients to pay a higher fee over a shorter treatment period? How will this affect the patient's ability to pay?

Further, the mechanism underlying any increased orthodontic tooth movement due to vibration remains unclear. Studies on a cellular level have shown a promising but complicated mechanism of how vibration may enhance activation of various cell proliferation and differentiation molecules within the periodontal ligament (PDL) stem cells as well as increase levels of gingival inflammation biomarkers.¹² For example, vibration therapy might accelerate breakdown of the cellular cytoskeleton, increase actinG trafficking into the nucleus, increase Runx2 gene expression, and thus facilitate bone formation.¹ Whether this mechanotransduction mechanism can be translated into clinical tooth movement is unknown and its clinical evidence remains to be elucidated.

In this study, we propose a randomized prospective clinical design to investigate effects of AcceleDent vibration therapy on the efficiency of tooth movement, on the activation of gingival crevicular fluid biomarkers and on patient discomfort in conjunction with accelerated Invisalign therapy.

Methods:

- 1. Study Design:

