 - a. In this study, we propose a single-blinded (Invisalign faculty) randomized prospective paralleled clinical trial to investigate effects of AcceleDent vibration therapy on the efficiency of tooth movement, on the activation of gingival crevicular fluid biomarkers and on patient discomfort in conjunction with accelerated Invisalign therapy. Enrolled subjects will be randomly allocated into one of 3 groups: Standard Invisalign therapy (G1-control), Accelerated Invisalign therapy + vibration (G2) and Accelerated Invisalign therapy without vibration (G3). Patients allocated to the standard Invisalign group will change aligners every 2

weeks while the both intervention groups will change aligners every 4 days. Patients allocated to the vibration group will receive an AcceleDent Aura device and bite down on the mouthpiece for 20 minutes/day. The AcceleDent Aura device vibrates at a .25N (25 grams) force level with a 30 Hz frequency. Data collection will include intra oral scans of both the maxillary and mandibular dentition at 5 different time points: TO (baseline), T1 (4 days), T2 (14 days), T3 (6 weeks) and T4 (12 weeks). In addition, PerioPaper strips will be used to sample gingival crevicular fluid at each of the time points listed above. Research subjects will also be asked to complete a daily diary regarding their pain level during treatment. Treatment plans for enrolled patients will be created using Invisalign's proprietary software: Clincheck Pro®. To reduce treatment plan variability and reduce potential sources of error, [name], who is an "Elite Top 1% Invisalign provider" and also a member of the exclusive North American Invisalign Clinical Advisory Board, will approve each treatment plan. [name] will also be blinded to any patients participation within the study in order to eliminate potential bias.

2. Recruitment:

- a. Participants will be conveniently recruited from the sample population of individuals seeking Invisalign orthodontic therapy within the UNC Graduate Orthodontic Clinic. Benefits for participants will include complementary vibration therapy using the AcceleDent Aura device, which is an estimated value of \$800. Financial reimbursement will also be offered to offset any parking fees associated with the study.
- 3. Power Analysis:

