 - a. Our study will have 3 groups for evaluation: G1 control (Invisalign on a 2week aligner schedule) and 2 intervention groups, G2 and G3 (each on an accelerated 4 days aligner schedule). The only difference between the intervention groups will be the use of vibration (G2 with vibration vs G3 without vibration). The expected rate of tooth movement for G1 will be .04mm/day (.25mm/week or .5mm/2 weeks) while the expected rate of tooth movement for G2 and G3 will be .28mm/day (.5mm in 4 days). The standard deviation is assumed 0.1 for three groups. Based on our sample calculation to achieve an adequate power, we will attempt to recruit a total of 42 patients to account for a dropout rate of 30%. Ideally, we would like to have a total sample size of 21 patients to ensure each of 3 study groups will have 7 patients, which will achieve more than 0.8 power even under a Bonferroni correction for multiple comparisons.
- 4. Randomization:
 - a. Our patients will be randomly allocated into the 3 groups based on a block randomization with size 6. The list will be independently generated by our study biostatistician.
- 5. Type I error and statistical significance:
 - a. P values less than .05 will be considered statistically significant in the overall test
- 6. Inclusion Criteria:
 - a. Males or females over the age of 18 years old desiring orthodontic treatment.

- b. Adult dentition with all upper and lower front teeth present and any premolar and molar combination in the upper posterior of two teeth on each side.
- c. Normal pulp vitality and healthy periodontal tissues as determined by intraoral exam.
- d. Good health as determined by medical history.
- e. Willingness and ability to comply with study procedures, attend study visits, and complete the study.
- f. The ability to understand and sign a written informed consent form, which must be signed prior to initiation of study procedures.
- 7. Exclusion Criteria:
 - a. Patient under the age of 18 years old
 - b. Patients diagnosed with systemic diseases such as diabetes, hypertension (high blood pressure), temporomandibular disorders (jaw disorders), or craniofacial syndromes.
 - c. Severe malocclusions that would require adjunctive procedures other than Invisalign. These include impacted teeth, closure of extractions spaces.
 - d. Significant periodontal disease (> 4mm pocket depth or >2 mm of recession on upper anterior teeth).
 - e. Active caries not under care of either a dentist or periodontist.

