 - a. Patients who experience an adverse event or reaction such as: uncontrolled pain or allergy will be disenrolled from the study and allowed to continue Invisalign therapy using the standard two-week aligner schedule. In addition, non-compliant patients will be disenrolled from the study and recommend to continue Invisalign therapy using the standard protocol.
- 10. Data Analysis:
 - a. Tooth leveling and alignment
 - i. Little's Index
 - b. Tooth rotations and translations
 - i. Euler's Law of Motion (6 degrees of freedom)
 - ii. 3D surface mapping
 - c. Alternative measurement options
 - i. Screw Method
 - d. Inflammation biomarkers within gingival crevicular fluid
 - i. ELISA
 - e. Orthodontic Pain Assessment
 - i. Faces Pain Scale
- 11. Statistical Analysis:
 - a. In order to complete statistical analysis for maxillary and mandibular dentition, we will compare the five time points within each group as well as the three groups across each time point.
 - b. Our primary statistical method will be a three-way repeated measurement ANOVA, with the main effects being: vibration, aligner schedule, and time. The ANOVA measurement will identify significant differences within the data and the post hoc comparison will determine which specific variables are involved. In order for a relationship to be considered statistically significant, the p-value must be less than .05.
 - c. One additional method for statistical analysis could be a survival analysis which would be more favorable in the case our study experiences a high volume of drop-outs during treatment.
- 12. Patient Confidentiality:
 - a. Records related to this research study that involve perennial information will only be accessible by the primary research committee and direct assistants. Records will be stored on encrypted, password-protected computer hard drives. A 3-digit code number will be used rather than the subject's name to identify the specific data related to his/her involvement in the study. Only the research investigators will have access to the file that links personal

information to the 3-digit codes, and this file will be stored in a separate location from the actual research data.

Project Timeline:

Item	Date
Study Design; IRB submission ([name])	Spring 2016
Background Research	March 2016
Loose conceptual framework	March 2016
Presentation	April 2, 2016
Protocol	May 16, 2016
IRB approval	May 2016
Select study population	August 2016
Clinical Trial	November 2016

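### Tooth movement is analysed without reference to planned movement or baseline crowding, so mm/day cannot show whether accelerated aligners track their plan, and the vibration contrast carries avoidable noise

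*Combined protocol and SAP*

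**What the plan says.** - **Measurement.** The Methods paragraph of the abstract says "tooth movement will be evaluated by superimposing digital models recorded at the specific time points". Section 10 (Data Analysis) lists Little's Index, then "Tooth rotations and translations" with six degrees of freedom and 3D surface mapping. Each is a comparison of one scan with another.
- **Model.** Section 11 (Statistical Analysis) specifies a three-way repeated-measures ANOVA, the "main effects being: vibration, aligner schedule, and time". It names no covariate.
- **Aim.** The Objective, the Specific Aims and section 3 (Power Analysis) speak of the rate of tooth movement. The end of the Background and section 1 (Study Design) speak instead of "effects of AcceleDent vibration therapy on the efficiency of tooth movement". Efficiency is not defined.
- **Planned movement.** Section 1 states: "Treatment plans for enrolled patients will be created using Invisalign's proprietary software". One blinded clinician approves every plan. The Clinical Trial Protocol section puts plan presentation and the baseline scan at Visit 3 and delivery of aligner 1 at Visit 4.
- **Expected rates.** Section 3 takes .5 mm per aligner in every group. For G1 this is .5 mm in 2 weeks. For the accelerated groups "the expected rate of tooth movement for G2 and G3 will be .28mm/day (.5mm in 4 days". G2 and G3 share one expected rate, and the SD is 0.1 in all groups.

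**The concern.** The two schedules deliver programmed movement at very different speeds. A comparison of raw movement between them therefore largely reflects how many aligners have been worn. The accelerated arms could lag far behind their plan and still show more millimetres per day than G1. A reader of the results could not tell a schedule that tracks well from one that does not.

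The comparison that isolates vibration is G2 versus G3. Both arms change aligners every 4 days, so vibration would be expected to show mainly in how much of the programmed movement is achieved. Patients differ in planned movement and in crowding at the start. With neither in the model, those differences go into the error term of a comparison that has 7 to 14 patients per arm.

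**Working it through.** **Inputs.** Aligner intervals are 14 and 4 days (section 1). Movement per aligner is .5 mm, the SD is .1 and there are 7 analysable patients per group (section 3). The Arms section gives 14 recruited per group. The SD has no printed unit and is taken as mm/day. Tests are taken as two-sided, with Bonferroni alpha .05/3 = .0167. Power is from the noncentral t with noncentrality d/(SD × √(2/n)).

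**1. The plan's own power.** The printed rates differ by .28 − .04 = .24 mm/day. At n = 7 the noncentrality is .24/(.1 × √(2/7)) = 4.49, and power at alpha .0167 is .94. The plan's claim of more than 0.8 is reproduced for G1 against an accelerated arm.

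**2. Schedule contrast at day 84.**

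| | G1 | G2/G3 |
|---|---|---|
| Aligners worn | 84/14 = 6 | 84/4 = 21 |
| Programmed movement | 6 × .5 = 3.0 mm | 21 × .5 = 10.5 mm |

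The Visit 8 delivery list agrees: it starts at aligner 7 for controls and 21 for the accelerated groups. If G1 expresses its whole plan, the accelerated arms equal it at 3.0/10.5 = 28.6% expression. At 50% they have moved 5.25 mm, or 5.25/3.0 = 1.75 times as far. Visit 8 is labelled 12 weeks, but its day count is 218 − 120 = 98 days after Visit 4. The break-even share does not depend on this, since it equals 4/14.

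**3. Is the schedule result certain to be significant?** At .5 mm per aligner the rates are .5/14 = .0357 and .5/4 = .125 mm/day, a difference of .0893. With SD .1:

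| n per arm | Power, alpha .0167 | Power, alpha .05 |
|---|---|---|
| 7 | .18 | .34 |
| 10 | .29 | .47 |
| 14 | .44 | .62 |

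Only the printed .28 mm/day gives near-certainty. It does not equal .5 mm in 4 days, and the two figures must be reconciled.

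**4. Precision of G2 versus G3.** The stated means differ by 0, so the power in step 1 does not apply here. Without adjustment, the difference detectable with 80% power at alpha .0167 is .197 mm/day at 7 per group and .130 at 14. Both exceed the .125 mm/day implied by .5 mm in 4 days.

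**5. What adjustment could gain.** A covariate with correlation rho to the outcome leaves a residual SD of .1 × √(1 − rho²). The documents do not give rho. The illustration assumes a difference of .08 mm/day, 10 per arm, and one degree of freedom spent on the covariate.

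| rho | Residual SD | Power, alpha .0167 | Power, alpha .05 |
|---|---|---|---|
| none | .100 | .23 | .40 |
| .25 | .097 | .24 | .41 |
| .5 | .087 | .31 | .50 |
| .8 | .060 | .63 | .80 |

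To gauge rho, suppose planned movement per aligner varies between patients with a CV of 20% to 40% (an assumption). Around .125 mm/day it contributes an SD of .025 to .050. That is (.025/.1)² = 6% to (.050/.1)² = 25% of the variance, or rho .25 to .5. A rho of .8 from this covariate alone would need an SD of .08, a CV of .08/.125 = 64%.

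**6. Scans that fall mid-aligner.** On the nominal days, G1 at day 4 is 4 days into a 14-day aligner. The accelerated arms are mid-aligner at day 14 (14/4 = 3.5) and week 6 (42/4 = 10.5). Week 12 is the only post-baseline scan at which both schedules have completed a whole aligner.

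**The case against.** Rate is the stated objective in three places, and efficiency is never defined as a share of the plan. Raw movement over time is therefore a legitimate outcome. This stands, and the point does not ask for mm/day to be replaced.

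The protocol also knows that the schedule alone may explain faster movement. The Background says so, and G3 exists to separate the two. That stands too, but G3 does not show whether accelerated aligners track their plan.

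A reader might infer that the schedule contrast is close to a foregone conclusion. The documents do not support this. Only the expected direction is built in: at .5 mm per aligner and SD .1, power under Bonferroni is .18 to .44 with 7 to 14 per arm.

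A reader might also infer that the vibration result is biased by case mix. It is not, because allocation is randomised; the cost is imprecision. The size of that cost is unknown. Section 1 uses a single approver "To reduce treatment plan variability and reduce potential sources of error", and severe malocclusions are excluded. Both should narrow the spread of planned movement by an amount that the documents do not show.

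Finally, simple adjustment has traps. Movement per aligner translates to mm/day with slope 1/14 in G1 and 1/4 in G2/G3. Baseline Little's Index is already one of the five analysed time points. A ratio needs a denominator for mid-aligner scans and is one more outcome to interpret. These objections are sound, and the fix has to meet them.

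**Conclusion.** The point holds in a limited form. The plan analyses raw scan-to-scan change only. It makes no use of programmed movement, although a plan exists for every patient, and it does not adjust for baseline crowding. Two consequences follow.

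- Raw mm/day cannot show whether the accelerated aligners track their plan, because those arms draw level with a fully tracking G1 at 29% expression. This rests on the protocol's .5 mm per aligner and on full expression in G1.
- The G2 versus G3 contrast carries noise that could be reduced. The gain may be negligible (.23 to .24) or large (.23 to .63). The .08 mm/day difference, the 10 per arm and the correlations are assumptions; only the SD is the plan's. A large gain should not be presented as expected, since it needs a correlation well above what a 20% to 40% CV would give.

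The change is worth making because it is cheap, and because the first consequence does not depend on the size of the correlation.

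**What to change.** 1. Keep mm/day as the tooth-movement outcome.
2. For G2 versus G3, prespecify adjustment for programmed movement per aligner and baseline Little's Index. Take programmed movement from the plan as fixed before allocation; the protocol does not say when randomisation takes place, so state this.
3. Use the post-baseline scans as the response in that model, so that baseline is not both covariate and outcome.
4. If G1 is in the same model, let the programmed-movement slope differ by schedule. Do not adjust G1 contrasts for cumulative programmed movement: the schedule determines it, and adjusting would remove the effect under study.
5. As a secondary measure, report achieved divided by programmed movement through the aligner stage worn at each scan. Prespecify a rule for scans taken mid-aligner, and place the main emphasis on week 12.

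The cost is obtaining planned values from the planning software and one or two degrees of freedom. The documents do not say in what form those values can be extracted, so confirm this first.

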 - f. Chronic daily use of any non-steroidal anti-inflammatory medication, estrogen, calcitonin, or corticosteroids.
 - **g.** History of use or current use of any bisphosphonate medication or other medication for treatment of osteoporosis.
 - h. Current smoker (must not have smoked in the last 6 months).
 - i. Failing to comply with research protocols
- 8. Arms:
 - a. Control Group (G1): 14 patients, standard Invisalign therapy with 2 week aligner schedule
 - a. Intervention Group (G2): 14 patients, accelerated Invisalign + vibration
 i. AcceleDent device 20 minutes/day per manufacturer's instructions

b. Intervention Group (G3): 14 patients, accelerated Invisalign + no vibration

- 7. Clinical Trial Protocol:
 - a. Visit #1: Clinical Screening with UNC Orthodontic Faculty (clinical purposes only)
 - i. Brief discussion of findings with patient and eligibility for Invisalign
 - b. Visit #2: Clinical exam and records (clinical purposes only), 30 days post visit #1
 - i. Completion of medical history
 - ii. Completion of extra and intra oral exams
 - iii. Completion of alginate impressions
 - iv. Photographs (extra and intra oral)
 - v. Xrays- Panoramic and Cephalometric
 - c. Visit #3: Treatment Plan Presentation (Experimental Baseline), 60 days post visit #1

- i. Clinical Procedures:
 - 1. Treatment plan presentation
 - a. Each treatment plan will be approved by [name] who will be blinded to a patient's study participation
 - 2. Invisalign impressions with PVS material
- ii. Research Procedures:
 - 1. Study recruitment
 - 2. Informed Consent
 - 3. iTero intraoral scan
 - 4. Completion of the Inclusion/Exclusion Case Report Form
- d. Visit #4: (120 days post visit #1/Day #1 of active treatment)
 - i. Clinical Procedures:
 - 1. Intraoral exam and intraoral photographs
 - 2. Deliver aligner number 1 and usage instructions
 - ii. Research Procedures:
 - 1. Deliver AcceleDent Aura device along with instructions
 - 2. Collection of gingival crevicular fluid biomarkers
 - 3. Completion of Faces Pain Scale
 - 4. Deliver daily diaries
- e. Visit #5: (125 days post visit #1/ Day #5 of active treatment)
 - i. Clinical procedures:
 - 1. Deliver aligners 2-4 to accelerate Invisalign groups and aligner schedule instructions
 - ii. Research Procedures:
 - 1. iTero intraoral scan
 - 2. Collection of gingival crevicular fluid biomarkers
 - 3. Completion of Faces Pain Scale and Adverse Event Form
- f. Visit #6: (134 days post visit #1/Day #14 of active treatment)

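### Until T1 (4 days) G1 and G3 receive the same treatment, so a prespecified contrast of G2 with G1 and G3 pooled would estimate the T1 vibration effect more precisely than the planned G2 versus G3

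*Combined protocol and SAP*

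**What the plan says.** Section 11 (Statistical Analysis), item a, sets the time points against each other within each arm and also compares "the three groups across each time point". Item b names as the primary method "a three-way repeated measurement ANOVA, with the main effects being: vibration, aligner schedule, and time", followed by post hoc comparisons; the abstract adds a Bonferroni correction. Neither item treats T1 differently from later time points, and no pooled contrast is planned.

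Under Study Design, "both intervention groups will change aligners every 4 days", against every 2 weeks in G1. The Clinical Trial Protocol section shows when that difference begins:

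- Visit #4 (day 1 of active treatment), all arms: "Deliver aligner number 1 and usage instructions".
- "Visit #5: (125 days post visit #1/ Day #5 of active treatment") is the T1 visit. Its clinical item is: "Deliver aligners 2-4 to accelerate Invisalign groups and aligner schedule instructions".
- Visit #6 (day 14): G1 receives its second aligner, and attachments are first placed.
- Visit #8 (12 weeks): G1 and G3 first receive vibration devices. The device line at Visit #4 names no arm, but Study Design and Visit #8 make clear that only G2 vibrates before then.

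The Hypothesis section concerns vibration alone: "We propose vibration therapy will accelerate orthodontic tooth movement, increase inflammation biomarkers and reduce pain for orthodontic patients".

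**The concern.** From day 1 to T1 the schedule factor has not yet acted. G1 and G3 have worn the same aligner number for the same time, without attachments and without vibration. A G1 versus G3 test at T1 therefore asks about a difference that the design sets to zero, while the question the trial was set up to answer, vibration against none, is estimated at T1 from G2 and one comparison arm although two equivalent ones exist.

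What is at stake is precision at one early visit. That matters here because the arms are small (14 recruited, 7 in the power target) and because the power calculation assigns G2 and G3 the same rate, so it offers no assurance about detecting a vibration effect at any visit.

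**Working it through.** **The plan's own power figure.** Power Analysis gives 0.04 mm/day for G1, 0.28 mm/day for G2 and G3, SD 0.1 and 7 per group, and claims power above 0.8 under Bonferroni. The difference is 0.28 − 0.04 = 0.24, or 2.4 SD. With alpha .05/3 = .0167 (three pairs and two-sided testing assumed), a two-sample t test has power 0.94, so the claim is reproduced from those inputs. It is power for accelerated against standard. For G2 versus G3 the assumed difference is 0.28 − 0.28 = 0.

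**What the model estimates at T1.** Let a be the G1 mean, s the schedule effect and v the vibration effect. The three occupied cells are

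- G1 = a
- G3 = a + s
- G2 = a + s + v

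Solving gives s = G3 − G1 and v = G2 − G3. G1 enters the error variance but not the estimate of v.

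**With the schedule effect zero through T1.** Setting s = 0 gives v = G2 − mean of (G1, G3). With n per arm and outcome variance σ²:

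- G2 versus G3: variance = σ²(1/n + 1/n) = 2σ²/n
- G2 versus pooled: variance = σ²(1/n + 1/(2n)) = 1.5σ²/n
- Variance ratio 1.5/2 = 0.75, a fall of 25%; SE ratio √0.75 = 0.866, a fall of 13%. Equivalently, the planned SE is 1/0.866 = 1.155 times the pooled one.
- For n = 14 the SE is 0.378 SD planned and 0.327 SD pooled.
- To match this, G2 and G3 would each need 4n/3 patients, or 14 × 4/3 = 18.7.

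**Power.** Noncentral t, two-sided. The planned contrast uses the three-group error df 3n − 3 (39 and 18). The pooled contrast uses 3n − 2 (40 and 19), since one parameter is dropped. The documents give no vibration effect size, so the effects in SD units are assumptions.

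| Per arm | Quantity | G2 vs G3 | G2 vs pooled |
|---|---|---|---|
| 14 | Detectable at 80% power, alpha .05 | 1.09 SD | 0.94 SD |
| 14 | Power at 0.5 / 0.8 / 1.0 SD, alpha .05 | 0.25 / 0.54 / 0.73 | 0.32 / 0.67 / 0.85 |
| 14 | Detectable at 80% power, alpha .0167 | 1.27 SD | 1.10 SD |
| 7 | Detectable at 80% power, alpha .05 | 1.58 SD | 1.37 SD |
| 7 | Power at 0.5 / 0.8 / 1.0 SD, alpha .05 | 0.14 / 0.29 / 0.43 | 0.18 / 0.38 / 0.54 |
| 7 | Detectable at 80% power, alpha .0167 | 1.88 SD | 1.62 SD |

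The overall three-group F test at T1 (2 df, 14 per arm, 1.0 SD) has power 0.75, against 0.85 for the pooled contrast.

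**Why pooling must stop at T1.** Once the schedules diverge, G2 − mean of (G1, G3) = v + s/2. Under the stated rates s = 0.24 mm/day, so the pooled contrast would carry a bias of 0.12 mm/day even if vibration did nothing.

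**The case against.** The strongest reply is that the planned analysis already answers the vibration question. Power Analysis says that vibration is all that separates G2 from G3, and the two arms share schedule and aligner number throughout. That stands. A reader might infer that T1 is the only assessment, or the cleanest one, at which vibration can be judged free of schedule, or that the plan throws the T1 information away. The documents do not support either reading: G2 versus G3 is free of schedule at T1, T2, T3 and T4, and G1 still enters the T1 analysis through the error variance and its own comparison with G2. Pooling adds precision, not validity.

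Other points have weight:

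- T1 follows four days of one aligner in a 12-week study and is not a named primary time point. This argues for a secondary contrast.
- Item a is worded for the dentition, and item b names main effects without a T1-specific schedule term. Applying the point to biomarkers and pain is therefore inference. But no other group analysis is given for those outcomes, and item a does call for group comparisons at each time point.
- Visit #5 lists aligner delivery ahead of the scan, fluid sample and pain score, without saying that this is the order followed. If aligner 2 were worn first, G3 would no longer match G1 on fluid and pain measures.
- Only the faculty member approving treatment plans is described as blinded, and no sham device is described. Pooling makes an unblinded pain comparison more precise, not less biased, and knowledge of the coming schedule could differ between G1 and G3.

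**Conclusion.** The point holds as one of efficiency. By protocol G1 and G3 are the same treatment until T1, and section 11 does not use this. Pooling them lowers the variance of the T1 vibration contrast by 25%. With 14 per arm, power at an assumed 1.0 SD rises from about 0.73 to 0.85; with 7, from about 0.43 to 0.54. Only large effects become detectable: at 0.5 SD power stays at or below 0.32, so this does not make T1 a well-powered test of vibration.

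The result rests on a common SD across arms, two-sided testing, vibration in G2 only before week 12, and T1 measurements taken before aligner 2 is worn. It does not extend beyond T1.

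**What to change.** In section 11:

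1. Prespecify a secondary 1-df contrast at T1, G2 versus pooled G1+G3, for tooth movement, gingival crevicular fluid biomarkers and pain, and for diary days 1–4. Let it replace the G1 versus G3 test at T1.
2. Use G2 versus G3 for vibration from T2 onward.
3. Report the G1 and G3 means at T1 side by side, descriptively.
4. State how these secondary contrasts sit within the Bonferroni correction.

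In the Visit #5 procedures, state that the scan, fluid sample and pain score are completed before aligner 2 is worn.

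The cost is a few sentences in section 11 and a note on assessment order at one visit; no patients, visits or measurements are added. The pooling must be specified in advance, since a choice made after seeing the T1 means would carry little weight. The downside is that its validity depends on the assessment order being kept, and the pooled pain result remains open to influence from patients knowing their arm.
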